**05DF2007 Kysse Clinical Study Protocol**

CCI

CCI

*Effective*

Effective date: 2023-02-01 07:38

Version: 2.0

GALDERMA  
EST. 1981

Title  
**05DF2007 Kysse Clinical Study Protocol**

CCI

CCI

*Effective*

Effective date: 2023-02-01 07:38

Version: 2.0

GALDERMA  
EST. 1981

Title  
**05DF2007 Kysse Clinical Study Protocol**

CCI

CCI

*Effective*

Effective date: 2023-02-01 07:38

Version: 2.0

GALDERMA  
EST. 1981

Title  
**05DF2007 Kysse Clinical Study Protocol**

CCI

CCI

Effective date: 2023-02-01 07:38

*Effective*

Version: 2.0

*Effective*

2023-02-01 07:38

Version: 2.0

GALDERMA  
EST. 1981

Title  
**05DF2007 Kysse Clinical Study Protocol**

CCI

CCI

s

*Effective*

Effective date: 2023-02-01 07:38

Version: 2.0

GALDERMA  
EST. 1981

Title  
**05DF2007 Kysse Clinical Study Protocol**

CCI

CCI

*Effective*

Effective date: 2023-02-01 07:38

Version: 2.0

## 1 Study Information

### 1.1 Background

This statistical analysis plan (SAP) describes the analysis variables and statistical procedures that will be used to analyze and report the results from Protocol 05DF2007 (v2.0), dated 02 FEB 2023.

The SAP was written in accordance with the recommendations outlined in the International Conference on Harmonisation (ICH) E9 Guideline entitled “Guidance for Industry: Statistical Principles for Clinical Trials” and the ICH-E3 Guideline entitled “Guidance for Industry: Structure and Content of Clinical Study Reports”.

#### 1.1.1 Study Design

This is a prospective, open-label, multi-center study to evaluate the safety and effectiveness of *Restylane Kysse* for lip augmentation and correction of perioral rhytids, if applicable, in subjects with both biological parents of full Chinese descent.

Approximately 50 subjects with a score of 1 (Very Thin) or 2 (Thin) on the Medicis Lip Fullness Scale (MLFS) will be enrolled. The upper lip and lower lip scores do not have to be equal as long as each score is either 1 or 2 at baseline.

Following the informed consent and screening process, eligible subjects will be injected in the lips by the investigator at baseline. The method of injection is at the discretion of the investigator and will be recorded. Sufficient amount of product should be injected to achieve optimal aesthetic improvement as determined by the investigator and subject. Optimal aesthetic improvement is defined as at least 1-point improvement from baseline using the MLFS and the best correction that can be achieved as agreed by the investigator and the subject.

Subjects in the US meeting the Wrinkle Assessment Scale (WAS) inclusion criteria may also receive optional treatment with *Restylane Kysse* in the perioral rhytids at baseline. Treatment of the upper perioral lines, vermillion border, philtral columns, Cupid’s bow, and/or oral commissures may be performed to obtain optimal aesthetic improvement, as agreed by the investigator and subject.

Touch-up treatment of the lips and perioral area, if treated at baseline, may be administered 4 weeks after baseline treatment if deemed necessary to obtain optimal aesthetic improvement; this decision should be agreed upon by the investigator and the subject. Touch-up treatment will not be performed if the subject has a disease or condition described in the exclusion criteria or is experiencing an ongoing treatment-related AE that, in the opinion of the investigator, would be worsened by touch-up treatment.

The recommended maximum injected volume per subject per treatment visit is 6 mL (i.e. 1.5 mL for the upper lip, 1.5 mL for the lower lip, and 3 mL for perioral area, if treated). Treatment will be performed according to the approved Instructions for Use (IFU).

Subjects will have in-clinic follow up visits at 2, 4, 8, 16, 24, 32, 40, and 48 weeks after the last injection. If a touch-up is deemed necessary and performed at 4 weeks post-baseline, a second 2-week and 4-week follow-up visits should be scheduled.

GALDERMA EST. 1981	Title 05DF2007 Statistical Analysis Plan (SAP)	CC I [REDACTED]
-----------------------	--	--------------------

### 1.1.2 Number of Subjects and Randomization

Subjects will be recruited from up to 5 study sites; 4 sites in the US [REDACTED].

Approximately 50 subjects of full Chinese descent will be included in the study. The study is open-label and is not randomized.

## 1.2 Study Objectives

### 1.2.1 Effectiveness Objectives

The effectiveness objectives are:

1. To evaluate the effectiveness of *Restylane Kysse* for lip augmentation as assessed by the investigator using the Medicis Lip Fullness Scale (MLFS) for the upper and lower lips.
2. To evaluate the aesthetic improvement of the upper perioral rhytids and oral commissures after treatment with *Restylane Kysse* as assessed by the investigator using the Wrinkle Assessment Scale (WAS). *Note: After baseline, WAS will only be assessed for subjects who have been treated in the perioral area.*
3. To evaluate the aesthetic improvement (overall appearance) of the upper and lower lips after treatment with *Restylane Kysse* as assessed by the subject and the investigator, independently, using the Global Aesthetic Improvement Scale (GAIS).

[REDACTED]

### 1.2.2 Safety Objectives

To evaluate the safety of *Restylane Kysse* for lip augmentation in Chinese subjects via assessment of:

- AEs at all study visits.
- Pre-defined, expected, post-treatment events reported during the first 28 days after treatment as recorded in the subject diary.
- Lip safety assessments as evaluated by a qualified staff member including:
  - Presence of any unexpected resistance by palpation of each lip at baseline and at each physical follow-up visit.
  - Lip texture and symmetry according to pre-defined methods, for each lip at baseline and at each physical follow-up visit.
  - Lip movement, function, and sensation (on three different locations per lip) according to pre-defined methods, at baseline and at each physical follow-up visit.

## 1.3 Effectiveness Assessments

For all assessments, baseline will be defined as the observation that is closest to but prior to study treatment on Day 1 for treated subjects. Change from baseline will be calculated as the value at a given time point minus the baseline value.

### 1.3.1 Medicis Lip Fullness Scale

The MLFS is a validated photograph-based outcome instrument that is designed specifically for quantifying lip fullness. Scoring of lip fullness (see Table 1 below) will be based on visual live assessment by the investigator at defined time points, and not on a comparison to the baseline

appearance. Change from baseline (Day 1, pre-treatment) in MLFS will be calculated for each post baseline assessment.

This study will assess the magnitude of lip fullness augmentation using the two separate 5-grade MLFS photo guides (one scale for upper lip and one scale for lower lip).

**Table 1. Medicis Lip Fullness Scale**

Grade	Description
1	Very Thin
2	Thin
3	Medium
4	Full
5	Very Full

### 1.3.2 Wrinkle Assessment Scale

The WAS is a validated photograph-based outcome instrument that is designed specifically for quantifying facial folds. Scoring of fold severity is based on visual assessment of the length and apparent depth of the wrinkle at a certain time-point. Scoring of the upper perioral rhytids and oral commissures according to Table 2 will be based on visual live assessment by the investigator at defined time points, and not on a comparison to the baseline appearance. Change from baseline (Day 1, pre-treatment) in the WAS will be calculated for each post baseline assessment.

After the baseline visit, WAS will only be assessed for subjects who have been treated in the perioral area.

**Table 2. Wrinkle Assessment Scale for Evaluation of Upper Perioral Rhytids and Oral Commissures**

Grade	Description
0	No wrinkles
1	Just perceptible wrinkle
2	Shallow wrinkles
3	Moderately deep wrinkle
4	Deep wrinkle, well-defined edges
5	Very deep wrinkle, redundant fold

### 1.3.3 Global Aesthetic Improvement Scale (GAIS)

The 7-graded GAIS will be used to assess the appearance of the lips (upper and lower lip combined) compared to what they looked like before treatment (see Table 3).

Investigator assessment: The investigator will rate, in a live assessment, the global aesthetic improvement of the lips using the following categorical scale and responding to the question:

“With respect to the appearance of the subject’s lips, how would you describe the result of the lip treatment compared to the photos taken before treatment?”

GALDERMA EST. 1981	Title 05DF2007 Statistical Analysis Plan (SAP)	CC I [REDACTED]
-----------------------	--	--------------------

The subject's photographs from pre-treatment are compared to live assessment during the present visit.

Subject assessment: Subjects will rate, in live assessment, the global aesthetic improvement of their lips using the following categorical scale and responding to the question:

“With respect to the appearance of your lips, how would you describe the result of the lip treatment compared to the photos taken before treatment?”

The subject's photographs from pre-treatment are compared to live assessment using a mirror during the present visit.

**Table 3. Global Aesthetic Improvement Scale (GAIS)**

Grade	Rating	Definition for Investigator
3	Very much improved	Optimal aesthetic result for the implant for this subject.
2	Much improved	Marked improvement in appearance from the initial condition, but not completely optimal for this subject.
1	Improved	The appearance is improved from the initial condition.
0	No change	The appearance is essentially the same as baseline.
-1	Worse	The appearance is worse than the initial condition.
-2	Much worse	Marked worsening in appearance from the initial condition.
-3	Very much worse	Obvious worsening in appearance from the initial condition.

CCI

#### 1.4 Effectiveness Endpoints

The effectiveness endpoints include:

1. MLFS change from baseline and response rates at 8, 16, 24, 32, 40 and 48 weeks after last injection.
2. WAS change from baseline and response rates at 8, 16, 24, 32, 40 and 48 weeks after last injection.
3. GAIS response rates at 8, 16, 24, 32, 40 and 48 weeks after last injection.

CCI

#### 1.5 Safety Assessments

The methods for collecting safety data are described in Section 7 of the Clinical Study Protocol. Data to be collected include the following:

- Adverse events.
- Subject diaries to be completed daily for 28 days following each treatment session.
- Lip Safety Assessments.
- Device deficiencies.
- Urine pregnancy test performed at screening and all treatment visits (prior to treatment).

- C [REDACTED]  
CI [REDACTED]
- [REDACTED]
  - [REDACTED]
  - [REDACTED]
  - [REDACTED]
  - [REDACTED]
  - [REDACTED]
  - [REDACTED]
  - [REDACTED]

## 2 Statistical Methods

### 2.1 General Methods

Any change made to the finalized SAP before database lock will result in an SAP amendment. Otherwise, changes will be documented in the Clinical Study Report (CSR). However, if additional supportive or exploratory analyses are requested after SAP approval, this will not require amendment of the SAP, but these additional analyses will be described in the CSR.

Some of the analyses detailed here may be more explicit or in some respects different from those stated in the protocol. In case of differences, this SAP supersedes the statistical sections in the protocol.

#### 2.1.1 Programming Conventions

EMB Statistical Solutions will have responsibility for performing analyses. All computations for statistical analyses will be performed using SAS® software, Version 9.4 or later. All SAS programs used in the production of statistical summary outputs will be validated with independent programming prior to finalization. In addition, all program outputs will be independently reviewed. The validation process will be used to confirm that all data manipulations and calculations were accurately done. Once validation is complete, a senior statistical reviewer will perform a final review of the documents to ensure the accuracy and consistency with this plan and consistency

GALDERMA EST. 1981	Title 05DF2007 Statistical Analysis Plan (SAP)	CC I [REDACTED]
-----------------------	--	--------------------

within tables. Upon completion of validation and quality review procedures, all documentation will be collected and filed by the project statistician or designee.

The electronic case report form (eCRF) data for all subjects will be provided in Standard Data Tabulation Model (SDTM) datasets. Analysis Data Model (ADaM) datasets will be developed from the SDTM datasets for use in table and figure production.

### 2.1.2 Reporting Conventions

The formats for the tables, listings, and figures described in this SAP will be provided in a companion document. Changes to the formats of these reports that are decided after the finalization of the SAP will not require an amendment. In addition, any additional supportive or exploratory analyses requested after SAP approval will not require amendment of the SAP. These additional analyses will be described in the CSR.

Study data from the eCRFs as well as derived variables will be provided in subject data listings. An indication of specific listings for each data type will not be indicated in the text of subsequent SAP sections. Data listings supplied as part of the CSR will be sorted by study site number concatenated with subject number, assessment dates, and/or time point.

The following conventions will be applied to all data presentations and analyses:

- Confidence intervals (CIs) will be two-tailed and constructed at a confidence level of 95%. Statistical tests will be performed at a significance level of 5%, and p-values will be two-sided, unless otherwise specified.
- Quantitative variables will generally be summarized by the number of subjects, mean, standard deviation, median, minimum, and maximum. Unless otherwise specified, the minimum and maximum values will be displayed to the same number of decimal places as the raw data, the mean and median will be presented to one extra decimal place compared to the raw data, and the standard deviation will be displayed to two extra decimal places compared to the raw data.
- Categorical variables will be summarized by the number and percentage of subjects (and number of events where appropriate) within each category. Unless otherwise specified, the percentage will be presented in parentheses to one decimal place. Frequency and percentage values of 0 will be presented as '0' rather than '0 (0)'.
- All summary tables will include the analysis population sample size (i.e., number of subjects) in each treatment group.
- Date variables will be formatted as DDMMYY for presentation.

### 2.1.3 Data Transformations

CCI

## 2.2 Analysis Populations

The statistical analyses will be performed based on the following subject populations.

### 2.2.1 Modified Intent-to-Treat (MITT) Population

The MITT population includes all subjects who were treated in both lips. All effectiveness variables will be analyzed based on the MITT population.

### 2.2.2 Safety Population

The Safety population includes all subjects who were treated with *Restylane Kysse* in at least one lip, and will be analyzed according to the treatment actually received. All safety data will be summarized descriptively based on the Safety population.

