### 3.4.2 Visit 2: Baseline/Day 1 (Treatment)

If the screening and baseline visits are not performed on the same day, the following procedures should be repeated:

- Record the subject's medical history (including any prior dermatological procedures or implants).
- Record the subject's prior and concomitant medications/procedures.
- Perform UPT for females of childbearing potential.
- Investigator assessment of lip fullness using the MLFS.
- For subjects in the US: Investigator assessment of perioral rhytid wrinkle severity using the WAS.

CCI

- Interview and assess for pre-treatment AEs.
- Re-confirm eligibility.

The following procedures should be performed at the baseline visit only:

CCI

- Obtain pre-treatment photography.
- Investigator to treat the subject with *Restylane Kysse* (upper and lower lips, and perioral rhytids, if eligible and agreed upon by the investigator and subject).
- Evaluate the subject for post-treatment AEs.
- Record post-treatment concomitant medications/procedures
- Evaluate for device deficiencies.

CCI

- Schedule the Week 2 visit (Visit 3).

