#### 4.4 Subject Identification Number

Prior to any study procedures being conducted, the subject must sign the informed consent form (ICF). Each subject who has signed the ICF will be assigned a screening number. Upon enrollment, each subject will be assigned a subject number that will be allocated in ascending order within each center. A screen failure is a subject who signed the informed consent but never enrolled (i.e. received treatment) in the study. For screen failures, the subject source documents should indicate which assessments have been made and the reason why the subject was determined to be a screen failure. A screen failure should not be re-entered in the study. A subject is considered enrolled when they have signed the ICF and been treated.

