#### 5.5.5.1 *Signs of Intravascular Injections*

Immediately stop the injection if a patient exhibits any of the following symptoms, including changes in vision, signs of a stroke, blanching of the skin, or unusual pain during or shortly after the procedure. Patients should receive prompt medical attention and possibly evaluation by an appropriate health care practitioner specialist should an intravascular injection occur.

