### 9.2 Analysis populations

The following populations will be defined:

- Modified Intention-to-treat (MITT)      Includes all subjects treated in both lips
- Safety    Includes all subjects treated in at least one lip

MITT population will be used for all effectiveness analyses. Safety analysis will be performed based on the safety population set.

The disposition of subjects will be presented in tables and/or figures as appropriate. The number of screened, treated, completed, and withdrawn subjects will be presented, as well as number of subjects in each analysis population set.

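### The Safety population requires a treated lip, so a US subject injected only in the perioral area before the session is abandoned is exposed and enrolled but absent from every safety summary table.

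*SAP*

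**What the plan says.** **Safety population.** SAP 2.2.2 includes subjects treated "in at least one lip, and will be analyzed according to the treatment actually received", and adds: "All safety data will be summarized descriptively based on the Safety population". Protocol 9.2 has the same rule: "Includes all subjects treated in at least one lip". The clause on treatment actually received has no effect in a single-arm study.

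**MITT population.** SAP 2.2.1: "The MITT population includes all subjects who were treated in both lips", and "All effectiveness variables will be analyzed based on the MITT population".

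**What may be injected.** Protocol 3.4.2 lists the baseline treatment areas as "upper and lower lips, and perioral rhytids, if eligible and agreed upon by the investigator and subject". The perioral area is optional and limited to qualifying US subjects (protocol 3.1, 5.5.3). Its recommended maximum is 3 mL of the 6 mL total per visit (protocol Table 3). Neither document says which area comes first.

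**When injection stops.** Protocol 5.5.5.1: "Immediately stop the injection if a patient exhibits any of the following symptoms". The signs listed are visual change, signs of stroke, blanching and unusual pain.

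**Who is enrolled.** Protocol 4.4: "A subject is considered enrolled when they have signed the ICF and been treated". There is no lip condition. Under protocol 3.5 an enrolled subject who discontinues is not replaced.

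**The concern.** The Safety population should contain everyone exposed to the product. Here exposure is defined by one anatomical area, while the protocol allows injection in two. The protocol's own stopping instruction is a route by which a subject can be exposed in the second area and not the first, so an acute reaction to the product can itself cause the exclusion.

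Incidence of related adverse events is the stated safety endpoint (protocol 2.1.1), and protocol 1.4 says the study is meant to support a future marketing application. Protocol 1.5 names intravascular injection as the source of the rare but serious risks. An event of that kind should not depend on injection order to be counted in the tables.

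The effectiveness set has a milder form of the same problem. A subject with one lip treated is in Safety but outside MITT. That subject is missing even from the separate rate for the treated lip, although SAP 2.4.3.1 plans upper-lip and lower-lip rates separately.

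**Working it through.** There is no plan figure to reproduce: both documents say that about 50 subjects was not a calculated sample size. The check is a classification exercise followed by an illustration of size.

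**Step 1. Classify an interrupted session by where it ended, assuming no later injection.**

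- Perioral area injected, no lip injected: enrolled (protocol 4.4), not in Safety, not in MITT.
- One lip injected: enrolled, in Safety, not in MITT.
- Both lips injected: enrolled, in Safety, in MITT.

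The first case is the gap. No other section of either document assigns such a subject to a set.

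**Step 2. Does missing-data handling recover the subject?** No. The MLFS sensitivity analyses in SAP 2.4.2 replace missing scores with 1 or 5, but they are described for endpoints evaluated in MITT. They do not restore subjects outside it.

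**Step 3. Size for safety.** Assume 50 subjects with any injection, one of whom is stopped after perioral injection only and is the only subject with that event. The intervals are exact (Clopper-Pearson) 95%, the method the SAP uses for response rates. They are given here for illustration, since the SAP plans no inference on safety.

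- All exposed subjects: 1/50 = 2.0%. Lower limit 1 − 0.975^(1/50) = 0.05%; upper limit, the 97.5th percentile of Beta(2, 49), = 10.65%.
- Set as defined: 0/49 = 0%. Lower limit 0; upper limit 1 − 0.025^(1/49) = 7.25%.
- With two such subjects: 2/50 = 4.0% (0.49 to 13.71%) becomes 0/48 = 0% (0 to 7.40%).

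**Step 4. How likely is any stopped session?** The documents give no stop rate. For an assumed per-subject rate r, the chance of at least one stop in 50 is 1 − (1 − r)^50:

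- r = 0.1%: 4.9%
- r = 0.5%: 22.2%
- r = 1%: 39.5%
- r = 2%: 63.6%

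These are upper bounds for the gap. It also needs a US subject with perioral treatment, given before either lip, and a session that is not resumed.

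**Step 5. Size for effectiveness.** Assume 45 responders among 49 MITT subjects and one further subject with a single treated lip.

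- Excluded, as planned: 45/49 = 91.8% (80.4 to 97.7%).
- Included, treated lip a non-responder: 45/50 = 90.0% (78.2 to 96.7%).
- Included, treated lip a responder: (45 + 1)/50 = 92.0%.

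The shift is −1.8 or +0.2 percentage points, so its direction depends on the subject's outcome.

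**The case against.** The strongest reply is that perioral-only exposure departs from the planned regimen. The protocol synopsis says all enrolled subjects are treated in both lips at baseline, perioral injection is an optional addition, and the safety objective is worded around lip augmentation. This makes the case unlikely but does not close it: the definition still turns on a treated lip, and the study design also covers correction of perioral rhytids (protocol 3.1).

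A reader might infer that the event would be concealed. The documents do not support that. SAP 2.5.2 lists all adverse events, and separately serious ones, without restricting the listings to the Safety population. Serious events go to the sponsor within 24 hours (protocol 7.1.2.1), and withdrawals are listed with reasons. Protocol 9.2 also reports the number treated beside the number in each set, so a discrepancy would be visible. What is lost is the event's place in the incidence tables, since a listing gives no denominator.

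A reader might also infer that every stop removes a subject. It need not. Protocol 5.5.5.1 stops the injection but does not say that the session ends, and protocol 5.5.5.4 describes massage until normal colour returns after blanching. The documents do not define treated for a partly injected lip. Neither set is tied to the baseline session, so a lip injected at Week 4 could bring a subject back into either one.

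Finally, a reader might infer that the MITT rule favours the product. Step 5 shows that this is not established for the per-lip rates: the treated lip may well respond.

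**Conclusion.** The point holds for the Safety population as a narrow, low-priority defect of definition. A stated rule can drop an exposed and enrolled subject from all safety summary tables because of a reaction to the product. The expected number is small (assumed 0 to 1 of 50), but with one such subject a related event falls from 2.0% to 0% in the incidence tables.

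This rests on four conditions: perioral injection in a US subject, given before either lip, a session abandoned before any lip is injected, and no lip injected later. The documents neither require nor exclude that order.

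The MITT point is secondary. Losing a treated lip from its own response rate serves no purpose, but the numerical effect is slight, its direction is uncertain, and no threshold in this descriptive study turns on it.

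**What to change.** In SAP 2.2.2, define the Safety population as all subjects who received any injection of study product in any area.

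For effectiveness, include a subject with one treated lip in the separate MLFS rate for that lip, and report the number of subjects with interrupted treatment. Counting such subjects as non-responders in the combined rate should be at most a sensitivity analysis. It departs from the observed-case rule in protocol 9.8 and SAP 2.4.2, and an untreated lip that is scored supplies its own observed value.

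The cost is a short SAP amendment before database lock, as SAP 2.1 provides; after lock, the change would be documented in the study report. No new data are needed. SAP 2.1 gives the SAP precedence over the protocol's statistical sections, so the wording of protocol 9.2 can follow at its next amendment. The downside is that some rates may look slightly less favourable. No change to injection order or to the stopping instruction is proposed.
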